- For Aim 1, to determine the target strain range, pilot subjects were classified as high and low responders (five and three subjects, respectively, based on observed 14 week changes in ultradistal BMC of $+2.57\%$ and $+0.51\%$). On average the high responders' peak Von Mises equivalent strains within the ultradistal volume were $3430\pm536\text{ }\mu\epsilon$, whereas the low responders' were $2125\pm432\text{ }\mu\epsilon$. Based on these results, we conclude strains below $1800\text{ }\mu\epsilon$ are unlikely to elicit a response, whereas we observed that strains above $3600\text{ }\mu\epsilon$ required forces in excess of 450 N for the average subject. Many women have difficulty applying this magnitude. Thus, targets of 1800 and $3600\text{ }\mu\epsilon$ were identified for this experiment.
- For Aim 2, the target strain magnitude, $3600\text{ }\mu\epsilon$, represents the largest strain magnitude that is achievable voluntarily by most female subjects. In our pilot subjects, this required a target force of $445\pm80\text{ N}$. Using the largest reasonable strain value maximizes the possible strain rate that is achieved with the impact loading group and maximizes the possibility that the loading elicits an osteogenic response. The strain rates that are assigned, $4500\text{ }\mu\epsilon$ and $36,000\text{ }\mu\epsilon$, respectively, are a function of the load application time generated with each of the two instruction sets. *The range of strain magnitudes produced using “slow” versus “impact” instruction sets represent nearly the entire range that can be voluntarily produced safely and consistently by subjects.*
- In both aims, subjects will apply 100 cycles of loading per day, 4 days per week, for 12 months. In our pilot subjects, this number of cycles per week was well tolerated by subjects and was osteogenic.

b. Sources of Materials

All research data will be obtained from the subjects specifically for research purposes.

- QCT data is uploaded to a secure cloud-based website (www.Lifelimage.com) for transfer to the laboratory. Per hospital procedure, all CT scans are read by a radiologist to ensure that no abnormalities are detected. Should the scan reveal abnormal pathology, the subject will be contacted directly by the radiologist. The CT scan is documented in each subject's medical record as a research CT scan.

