Statistical Analysis Plan

A Prospective Study of Human Bone Adaptation Using a Novel in Vivo Loading Model

ID: 13-111

NCT #: not yet assigned

Originally created: 1/12/2012

Last updated: 1/12/2012 by [name]

Statistical Analysis Plan

Originally created: 1/12/2012

Last updated: 1/12/2012 by [name]

Statistics and Expected Outcomes:

An intent to treat analysis will not be employed here because the purpose of this research is to determine the link between *actual strains applied to bone* and the bone adaptive response. The present study is not intended to address the degree to which mechanical loading is an effective means to improve bone strength in a public health setting. Accordingly, adherence to the mechanical loading protocol is expected to influence the degree of adaptation and will be considered a potential explanatory variable for the following analyses.

For Experiment 1, hypotheses are related to the effect of strain magnitude.

For Experiment 2, hypotheses are related to the effect of strain rate. In both cases, the statistical analysis plan is the same, but tests will be performed on the corresponding variables (strain magnitude, or strain rate).

Hypothesis 1a: Bone mass will increase proportionally to the applied strain.

This hypothesis will be tested in two ways. In the first analysis, subjects will be analyzed by group (control, low, and high strain magnitude groups). For the group analysis, the 12-month change in whole radius total BMC will be analyzed as the primary dependent variable in a linear regression model with coefficients representing contrasts between each of the two experimental groups and the control group. Secondary outcome measures of trabecular BMC, ultra-distal BMC, fracture strength, moments of inertia, and others, will also be compared between groups using regression models for change scores at each of the four time points.

If our hypothesis is supported then there will be little change in the control group, a small but significantly higher increase in the 1800 $\mu\epsilon$ group, and a large and significantly higher increase in the 3600 $\mu\epsilon$ group. Similar models will be fit predicting change from baseline to 3, 6, and 9 months.

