If our hypothesis is supported, we would expect to observe significant strain-dependant increases in each of the variables listed for the experimental groups, but not in the control group.

Hypothesis 1d: Local regions experiencing high strain magnitudes will experience greater local increases in BMC than regions experiencing low strain magnitudes.

This hypothesis will be tested using only subjects in the experimental conditions. For each subject, all of the elements within the baseline FE model will be divided into quartiles based on actual Von Mises equivalent strain occurring within each element. Of interest for the present analysis are elements in the highest strain quartile and the lowest strain quartile. (Note that Von Mises equivalent strains always have a positive sign.) For each of these quartile groups the change in QCT voxel density for those voxels corresponding to the location of the elements will be determined. We will use a Student's t-test to compare the average voxel density change in high strain versus low strain quartiles.

If our hypothesis is supported then elements experiencing the highest Von Mises strain will have significantly greater increases in density compared to elements experiencing the lowest Von Mises strain. Our underlying assumption in using the highest and lowest quartiles is that a minimum strain threshold is required to initiate an increase in density. Therefore, including all elements in the analysis, most of which do not exceed this threshold, may make it difficult to detect a local effect, if one is present.

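### Neither Hypothesis 1a test separates more strain from any loading at all, because 3600 is never compared with 1800 microstrain; the documents also disagree on the response expected at 1800

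*SAP*

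**What the plan says.** SAP, Hypothesis 1a, states the hypothesis as "Bone mass will increase proportionally to the applied strain" and tests it in two ways.

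- **Group analysis.** The primary outcome is 12-month change in whole radius total BMC, in a linear regression "with coefficients representing contrasts between each of the two experimental groups and the control group". If the hypothesis is right, the SAP expects little change in controls, "a small but significantly higher increase in the 1800" microstrain group, "and a large and significantly higher increase in the 3600" microstrain group. No comparator is named for the last of these, and no 3600-versus-1800 contrast is listed.
- **Continuous analysis.** Change at all four time points is regressed on the strain each subject actually achieved, with control strain set to zero. Support means a significant strain coefficient.

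The SAP applies the same plan to strain rate in Experiment 2.

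Protocol, Section 1a, Rationale for Doses, concludes from pilot data that strains below 1800 microstrain "are unlikely to elicit a response", and sets the low target at that value. Group sizes (Protocol, Group Assignment) are 20 per loading group and 20 controls.

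**The concern.** Aim 1 manipulates strain magnitude, so its question is whether more strain gives more bone. Two comparisons with an unloaded control answer a different question: whether each loading regimen does anything. If both regimens worked equally well, both contrasts could be significant and the fitted slope through zero-strain controls would be positive. The trial could then report a strain-magnitude effect that its data do not show. The expected ordering, small at 1800 and large at 3600, is described but not tested.

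The second difficulty concerns the low group. The SAP expects a significant gain at a level that the protocol's dose rationale places at the edge of response. If the true response there is nil, the expected group pattern will almost never appear, however strong the effect at 3600. A reader could then wrongly take the missing low-group difference as evidence against any strain effect.

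**Working it through.** The documents give no power calculation, significance level or SD of BMC change, so there is no sponsor figure to reproduce. Assumptions: two-sided 5% tests with success counted only in the upward direction, normal outcomes, equal variances and no dropout.

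**1. Response expected at 1800.**
- Proportionality: 1800 / 3600 = 0.5, so half the 3600 effect.
- Pilot means (Rationale for Doses): +0.51% at 2125 microstrain and +2.57% at 3430. Slope = (2.57 − 0.51) / (3430 − 2125) = 2.06 / 1305 = 0.00158% per microstrain. The line reaches zero at 2125 − 0.51 / 0.00158, or about 1802 microstrain.

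This line is indicative only. The pilot groups were formed by outcome ("five and three subjects, respectively, based on observed 14 week changes in ultradistal BMC of" +2.57% and +0.51%), at 14 weeks and on ultradistal rather than whole radius BMC.

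**2. Group contrasts.** The standard error of a difference between two means of 20 is SD × √(2/20) = 0.316 SD. With 57 residual degrees of freedom the critical t is 2.002, so a difference must exceed 2.002 × 0.316 = 0.633 SD. A true 1 SD difference is then significant in about 87% of trials. The two control contrasts share one control group, and for a 1 SD gain in both groups they succeed together in about 80%.

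**3. Slope test.** As a one-time-point stand-in for the continuous analysis, regress change on assigned strain 0, 1800, 3600. With equal groups and equal spacing, slope = (mean at 3600 − mean in controls) / 3600. The 1800 group drops out of the estimate and affects only the residual variance. The test therefore cannot tell a plateau from a threshold.

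**4. Simulation,** 200,000 trials per scenario. Gains over control are in SD units.

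| True gain at 1800, 3600 | Both control contrasts | Slope test | 3600 > control and 3600 > 1800 |
|---|---|---|---|
| 1, 1 (equal gains) | 80% | 86% | 2.5% |
| 0, 1 (no response at 1800) | 2.5% | 86% | 80% |
| 0.2, 1 (pilot ratio 0.51 / 2.57) | 9% | 87% | 66% |
| 0.5, 1 (proportional) | 33% | 87% | 33% |

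**5. Range over the unknown SD.** Take 2.57 percentage points as the 3600 effect and let the SD run from 1 to 3 percentage points (40,000 trials each).
- Equal gains: both control contrasts 100% to 64%, slope 100% to 75%, rule with 3600 above 1800 about 2.5% throughout.
- No response at 1800: both control contrasts about 2.5% throughout, slope 100% to 75%.
- Pilot-like (0.51 and 2.57): both control contrasts 36% to 7%.
- Proportional (1.285 and 2.57): both control contrasts 98% to 25%.

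**The case against.** The strongest reply is that a reader might infer too much. Four stronger readings are tempting, and the documents do not support them.

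- **That the plan fails when the sponsor's own theory is right.** Hypothesis 1a states proportionality, under which a gain at 1800 is expected. The SAP does say that "a minimum strain threshold is required to initiate an increase in density", but under Hypothesis 1d and about local elements of the finite element model, not whole radius BMC by group.
- **That the protocol expects no response at 1800.** It speaks of strains below 1800. A nil response at 1800 is an inference from eight pilot subjects.
- **That the SAP sets a decision rule which equal gains satisfy.** The text describes an expected pattern, and two equal gains do not fit small versus large. If significantly higher at 3600 means higher than the 1800 group, equal gains would meet all three comparisons in only about 1% of trials. That reading still needs a contrast the SAP does not list. If only the observed means must be in order, equal gains pass in about 40%.
- **That 3600 above 1800 should replace the 1800-versus-control comparison.** Under proportionality the two rules do equally well (33% each). The replacement would also declare support in about 80% of trials with no response at 1800, which is not proportional either. That is a choice between hypotheses, not a correction.

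The continuous analysis also protects Hypothesis 1a against a threshold, and it uses actual strains and four time points, which the stand-in does not. What stands is that it does not distinguish equal gains from a graded response.

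**Conclusion.** The point holds in two parts. First, neither Hypothesis 1a test as written distinguishes a strain-magnitude effect from loading versus no loading. With equal 1 SD gains and 20 per group, the group contrasts succeed in about 80% of trials and the slope stand-in in about 86%, against about 2.5% once 3600 must also exceed 1800. The percentages depend on the assumed SD; the inability to separate the two explanations does not.

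Second, the SAP and the protocol's dose rationale give different pictures of the response at 1800. If it is truly nil, the expected group pattern appears in about 2.5% of trials. This does not mean that Hypothesis 1a as a whole must then fail, because the slope test would usually pass.

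The missing contrast carries over to slow versus impact in Experiment 2. The argument about the 1800 boundary does not, since both rate groups there target 3600 microstrain.

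**What to change.** 1. Add the high-versus-low contrast to the regression already planned: 3600 versus 1800 in Experiment 1, impact versus slow in Experiment 2. It is the difference between two coefficients already estimated.
2. Require that contrast before claiming an effect of strain magnitude or strain rate. A loaded-versus-control difference alone supports an effect of loading.
3. Report 1800 versus control as an estimate with a confidence interval, and state that a non-significant result there is not by itself absence of a strain effect.
4. Reconcile the protocol's dose rationale with SAP Hypothesis 1a on the response expected at 1800. No change to any target is proposed.

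The cost is SAP wording and one extra contrast, with no new data. Requiring the contrast does limit what can be claimed: under proportionality with 1 SD at 3600, 3600 would be shown above both control and 1800 in about 33% of trials. The interval for this contrast should therefore be reported whatever its significance.

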Furthermore, future work that involves populations with known differences in bone metabolism, such as those on anabolic or antiresorptive therapy, lactating women, adolescents, or those with recent healing fractures, would allow us to elucidate the degree to which adaptation is altered by these differences in bone metabolism. Our experimental approach involves upper extremity loading, which directly improves the bone mass and structure of the distal radius. This may provide research subjects with long-term skeletal health benefits at the distal radius, and this approach may serve as a basis for a new bone strengthening regime that targets this common fracture site.

5. Data and Safety Monitoring Plan

This study is considered to be over all low risk. The experimental treatment, mechanical loading, is voluntary and has been well tolerated by subjects in the past. The data collection methods involve some risk in that there is radiation exposure. Subjects' decision making capabilities are not expected to be affected by their participation in this study.

The Principal Investigator, [name], and Co-investigator, [name], will monitor data and safety. Each month Drs. [name] and [name] will review the available data on subject compliance, data collections, drop outs, and any reported adverse events. Observations and comments from subjects will also be noted. Special attention will be paid to drop outs and the reason for drop outs, since this may be an early indicator that the mechanical loading is not well tolerated by subjects.

The magnitude of mechanical loading prescribed to each subject will be decreased if the subject is having difficulty achieving the magnitude or if she experiences pain during or after loading. If more than two subjects experience pain the dose of mechanical loading will be decreased for all subjects. In no case will the mechanical loading dose be increased beyond the planned 100 cycles per day, 4 days per week and 450 N.

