In the second analysis, we will consider the *actual* strain magnitudes achieved by each subject, (which may differ from the group assigned strain), as a continuous variable, and will set the strain magnitude for control subjects to zero. The underlying assumption in doing this is that the baseline daily activity for *all* subjects is approximately equal, and is sufficient to maintain bone homeostasis. For this analysis, all four time points will be combined into a single model to examine changes across time after the loading regime has ended, and to compare the levels of applied strain. The dependent variable is the change score (in whole radius total BMC) from baseline; the independent variables are level of strain, time (3, 6, 9, 12 months), and a random intercept term for each subject to handle collinearity within repeated measurements. As in the first analysis method, secondary outcome measures of regional BMC, fracture strength, and others, will be considered as well.

If our hypothesis is supported then strain magnitude will be a significant predictor of change in whole radius total BMC and other related variables.

Hypothesis 1b: High initial bone mass, physical activity levels, and grip strength will be associated with diminished adaptive response for a given strain magnitude.

To test this hypothesis, initial BMC, grip strength, and physical activity will be added as potential covariates for the statistical models described in Hypothesis 1a.

If our hypothesis is supported then we would expect to observe an inverse relationship (negative coefficient) between initial bone mass, physical activity, grip strength, and change in BMC per group or per unit applied strain.

Hypothesis 1c: Bone structural changes will include increases in cortical diameter and thickness, and increased trabecular bone mass near the endosteal surface.

To test this hypothesis, the following variables will be examined:

For cortical diameter and thickness: integral and cortical bone mass and bone volume, compressive and bending strength index, and cross-sectional moments of inertia (bending and torsional)

For trabecular bone: trabecular bone mass and volume, cross sectional trabecular moments of inertia

Using the methods described for testing hypothesis 1a, changes in each of the specific variables listed will be examined at each time point. Here, the primary interest is in which specific quantities show the largest strain-related change.

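### The primary group contrast regresses 12-month change on its own, so early leavers drop out of it and their interim values are unused; if dropout is related to response, the contrast could be overstated

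*SAP*

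**What the plan says.** SAP, Hypothesis 1a, first analysis: "the 12-month change in whole radius total BMC will be analyzed as the primary dependent variable in a linear regression model", with each loading group contrasted with control. For the earlier visits, "Similar models will be fit predicting change from baseline to 3, 6, and 9 months". Secondary outcomes are handled the same way, "using regression models for change scores at each of the four time points".

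SAP, opening paragraph of Statistics and Expected Outcomes: "An intent to treat analysis will not be employed here". No other analysis set is defined there. Adherence is named as a possible explanatory variable. Neither document gives a missing-data method or a dropout allowance.

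SAP, Hypothesis 1a, second analysis: here "all four time points will be combined into a single model", with "a random intercept term for each subject to handle collinearity within repeated measurements". Its exposure is the strain each woman achieved, with controls set to zero, not her group.

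Protocol section 5 (Data and Safety Monitoring Plan): dropouts and their reasons are to be watched closely, "since this may be an early indicator that the mechanical loading is not well tolerated by subjects".

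**The concern.** A regression of 12-month change can use only women with a month-12 value. A woman who leaves after month 6 counts in the 3- and 6-month models and is absent from the primary one. The four visit models can therefore describe different sets of women, and an apparent time course across them may partly reflect who stayed.

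The control group is observed only, so intolerance of loading can remove women from the loaded groups alone. The SAP expects adherence to influence adaptation. A woman who struggles, loads less and leaves may well have been gaining less than her group's average. If so, the women still present at month 12 are the better responders, and the loaded-versus-control difference is too large. With 20 women per group, a few such losses matter.

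**Working it through.** **What the documents supply.** Group size is 20 (Protocol, Introduction). There is no stated dropout rate, SD of change, between-visit correlation or power calculation, so there is no plan figure to reproduce. What follows is illustration on assumed inputs.

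**1. Bias, two-visit illustration.** Assumptions: 20 per arm; month-12 change with SD 1; true loaded-minus-control difference 1.0 SD; correlation 0.7 between month-6 and month-12 change; dropout after month 6 in one loaded arm only. The dropout model is

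log-odds of leaving = a − slope × (month-6 change minus arm mean, in SD),

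with a set so that about 24–25% leave. The completer estimate is the difference in month-12 means among women with a value. The likelihood estimate adds b × (arm mean at month 6, all women, minus the mean among completers), where b is the within-arm regression slope of month 12 on month 6. Each row is 20,000 simulated trials.

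| Slope per SD (odds ratio) | Lost | Completers | Likelihood |
|---|---|---|---|
| 0 (1.0) | 24% | 1.00 | 1.00 |
| 0.5 (1.6) | 24% | 1.08 | 1.00 |
| 1.0 (2.7) | 25% | 1.15 | 1.00 |

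The slope creates the bias. The completer bias equals the correlation times the shift in completers' mean month-6 change: at slope 1.0 the shift is about 0.21 SD, and 0.7 × 0.21 = 0.15. The standard error of the contrast is about 0.34, so this bias is 0.15 / 0.34 = 0.44 of a standard error.

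**2. When dropout depends on what is not seen.** The likelihood estimate of 1.00 above follows from letting dropout depend only on the month-6 value the model uses. If dropout instead depends on the month-12 value itself (slope 1.0, about 25% lost), completers give 1.22 and the likelihood estimate 1.11 to 1.12 between runs. About half the bias remains.

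**3. Four-visit illustration.** Dropout can follow months 3, 6 or 9 in the loaded arm; slope 1.0; SD 2.0 points (assumed); correlations 0.5 to 0.85. The true difference is 2.57 − 0.51 = 2.06 points. It comes from the pilot responder split in the Protocol's Rationale for Doses: eight women, ultradistal BMC, 14 weeks. It serves for scale only.

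| Lost from loaded arm | Completers | Overstatement | All-visit likelihood |
|---|---|---|---|
| about 14% | 2.20–2.29 | 7–11% | 2.05–2.07 |
| about 26% | 2.30–2.47 | 12–20% | 2.05–2.06 |
| about 35% | 2.42–2.63 | 17–28% | 2.06–2.07 |

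With dropout unrelated to response, neither estimate is biased, and using all visits lowers the standard error by only about 1–7%.

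**4. Precision.** With a fraction m = 0.25 missing at random in the loaded arm, using the earlier value multiplies the variance of that arm's mean by 1 − ρ²m. The control arm gains nothing. In units of σ², the completer contrast has variance 1/15 + 1/20 = 0.1167.

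- ρ = 0.5: 0.9375/15 + 0.05 = 0.1125, a fall of 4%.
- ρ = 0.7: 0.8775/15 + 0.05 = 0.1085, a fall of 7%.
- ρ = 0.9: 0.7975/15 + 0.05 = 0.1032, a fall of 12%.

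**5. Are interim BMC values available?** The SAP's second analysis names change in whole radius total BMC at 3, 6, 9 and 12 months. Protocol section 1c counts one CT per arm in each 12-month period, plus four and then three HR-pQCT scans per arm. The dose totals confirm those counts: 0.05 + 2×9 + 2×4×0.3 = 20.45 mrem and 2×9 + 2×3×0.3 = 19.8 mrem. The documents do not say which scanner supplies whole radius total BMC. If it is HR-pQCT, interim values can exist; if it is CT, values at 3, 6 and 9 months do not fit that count.

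**The case against.** A reader might infer that the protocol predicts dropout from intolerance. It does not: section 5 says only that dropout may be an early sign, and the same section reports that loading was well tolerated in the past. Other provisions work against such dropout: women who cannot reach 300 N at screening are ineligible, force is built up over four weeks, and load is reduced for difficulty or pain. This stands. Dropout related to response is a recognised risk, not a stated expectation.

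Hypothesis 1a is tested in two ways, and the mixed model in the second analysis can keep women with partial follow-up. It also serves the SAP's stated purpose, the response to strain actually applied. This limits the consequence, but a model of achieved strain does not repair the contrast between groups. Adjusting for adherence cannot restore a woman who has no month-12 outcome.

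Intent to treat was rejected on purpose, so including every woman with follow-up may seem at odds with the SAP. It need not be. Under missing at random, the likelihood model estimates the response had women stayed, which is closer to the SAP's biological question than the result in a self-selected group of completers. The SAP should say so.

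Finally, the likelihood model is not a full remedy. Pain or struggling with the load need not show in an earlier BMC value. This also stands, and it is why a further sensitivity analysis is needed.

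**Conclusion.** The point holds as a risk of bias. The primary group contrast excludes women without a month-12 value, makes no use of their earlier values, and has no missing-data method behind it. If women who leave a loaded group tend to be lower responders, the contrast is overstated: by about 8% or 15% at the moderate and strong slopes in the two-visit illustration, and by nothing if dropout is unrelated to response. The size rests on assumed dropout, correlation and, above all, the dropout slope.

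It would go too far to say that the contrast is biased, that a likelihood model removes all bias, or that much precision is lost. The documents give no dropout figures; the model corrects fully only for dropout explained by observed values; and the variance of the contrast falls by only about 4–12%. Nor can one say outright that the interim data are already scheduled, until the scanner that supplies the primary measure is named. This is a cheap improvement.

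**What to change.** 1. Replace the four separate group regressions with one likelihood-based repeated-measures model of BMC change at 3, 6, 9 and 12 months, with group, visit, group-by-visit and within-woman correlation. Use every woman with at least one follow-up value. Take the month-12 low-versus-control and high-versus-control contrasts as primary, and read the 3-, 6- and 9-month contrasts from the same model.
2. State that this estimates the response had women stayed, under missing at random, and explain how that fits the rejection of intent to treat.
3. Keep the 12-month completer regression as a sensitivity analysis. Add one in which dropout for pain or intolerance may be related to unseen response.
4. State which scanner supplies whole radius total BMC. If it is CT with no values at 3 to 9 months, replace step 1 with multiple imputation of month-12 BMC, using the interim HR-pQCT measures and adherence as predictors.

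Cost: SAP wording, provided that interim values or interim HR-pQCT measures exist as scheduled; the SAP already plans a repeated-measures model of this kind. A covariance structure or an imputation model must be chosen, at a small cost in degrees of freedom.

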- For Aim 1 the low and high groups refer to low and high strain magnitude. Subjects in each of these groups will be assigned a target force based on their individual anatomy and their group assignment. The low and high strain groups will be assigned strain magnitudes of 1800 micro-strain ($\mu\epsilon$) and 3600 $\mu\epsilon$ respectively. The forces required to produce these strains typically range from 300 to 500 N (0.5 to 0.8 body-weights).
- For Aim 2 the low and high groups refer to low and high strain rate. Subjects in each of these groups will be assigned a target force based on their individual anatomy, and will be given one of two instruction sets that will assist subjects in producing slower or more rapid forces. The slow strain rate group will be given a target loading rate of 4500 $\mu\epsilon/s$ (i.e., 3600 $\mu\epsilon$ achieved in 0.8 seconds. The impact strain rate group will be given a target loading rate of 36,000 $\mu\epsilon/s$ (i.e., 3600 $\mu\epsilon$ achieved in 0.1 seconds). The slow group will be instructed, "Each time you hear a beep, lean on your hand to reach the target force, loading and unloading your hand as slowly and evenly as possible." In pilot subjects, this resulted in a load application time of 0.8 seconds. The impact group will be instructed to "Stand approximately 15 inches away from the device (which is placed on a hip-high table). When you hear a beep, fall forward until your hand contacts the load cell. You may need to adjust how close you stand to achieve your target force." In pilot subjects this resulted in a load application time of 0.1 seconds. Subjects in the control group will continue their regular physical activity.

Rationale for Doses:

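### Experiment 2 names no impact-versus-slow test, and its continuous model with controls at zero can credit strain rate with the effect of loading itself

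*SAP*

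**What the plan says.** The SAP (Statistics and Expected Outcomes) writes out one plan, for strain magnitude, and carries it over: "For Experiment 2, hypotheses are related to the effect of strain rate", and "In both cases, the statistical analysis plan is the same, but tests will be performed on the corresponding variables (strain magnitude, or strain rate").

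Under Hypothesis 1a that plan has two parts.

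- **Group analysis (primary).** The 12-month change in total BMC of the whole radius is regressed on group, with "coefficients representing contrasts between each of the two experimental groups and the control group". The expected result is that "there will be little change in the control group, a small but significantly higher increase in the 1800" microstrain group, followed by a large and significantly higher one in the 3600 group. The comparator for that last increase is not given.
- **Continuous analysis.** Achieved strain is the predictor, and the plan "will set the strain magnitude for control subjects to zero". The other terms are time and a random intercept per woman. The hypothesis counts as supported if "strain magnitude will be a significant predictor of change in whole radius total BMC".

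The Protocol (Group Assignment) states: "For Aim 2 the low and high groups refer to low and high strain rate". Both groups aim for 3600 microstrain, reached in 0.8 s or 0.1 s. Rationale for Doses explains the shared target: it "represents the largest strain magnitude that is achievable voluntarily by most female subjects".

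**The concern.** Control women in Experiment 2 differ from the impact group in two ways: they are not loaded, and they have no loading rate. A comparison that includes them therefore carries the effect of loading to 3600 microstrain together with any effect of loading quickly. Only impact versus slow holds the target magnitude fixed while rate changes.

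The plan names no such comparison for the primary outcome. The continuous model has no term to absorb the loading effect, so its slope mixes loaded versus not loaded with fast versus slow. The Protocol expects loading to be osteogenic in itself, which is exactly the condition under which this rule misleads. Experiment 2 could report a strain-rate effect when both loaded groups gain equally, or when impact gains somewhat less than slow.

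**Working it through.** **Inputs from the documents.** Loading groups of 20 and a control group of 20 (Protocol, Group Assignment); all 20 controls are used as the comparator. The target rates reproduce: 3600/0.8 = 4500 and 3600/0.1 = 36,000 microstrain/s. The total also reproduces: 2 aims × 2 loading groups × 20 + 20 = 100.

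**Assumptions, because the documents give no figure.** Two-sided alpha 0.05, residual SD of change 1, loading gain D in SD units, 15% coefficient of variation in achieved rate, no dropout. Rejection is counted in the positive direction, so the nominal rate is 2.5%.

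**Step 1: bias with no rate effect.** Take x = (0, 4500, 36,000) and mean gains (0, D, D), with equal group sizes.

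- Mean of x = 40,500/3 = 13,500.
- Sum of squares per woman-triplet = 13,500² + 9,000² + 22,500² = 769,500,000.
- Cross-product = (−9,000 + 22,500) × D = 13,500D.
- Slope = 13,500D/769,500,000 = 1.754 × 10⁻⁵ D.
- Implied impact-minus-slow difference = slope × 31,500 = 0.553D. The true difference is 0.

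**Step 2: how often the support rule is met with no rate effect.** One 12-month score per woman, 20,000 replicates:

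| D (SD) | Slope as planned | With loaded indicator | Loaded women only | Impact vs slow |
|---|---|---|---|---|
| 0 | 2.4% | 2–3% | 2–3% | 2–3% |
| 0.5 | 17.4% | 2–3% | 2–3% | 2–3% |
| 0.8 | 35.4% | 2–3% | 2–3% | 2–3% |
| 1.0 | 50.2% | 2–3% | 2–3% | 2–3% |
| 1.5 | 81.2% | 2–3% | 2–3% | 2–3% |

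**Step 3: the planned four-time-point form.** With complete data and a strain level constant within each woman, the strain coefficient in the random-intercept model equals a regression on subject means (58 df). At D = 1.0 (4,000 replicates):

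| Within-woman correlation | Gain constant from month 3 | Gain builds linearly to month 12 |
|---|---|---|
| 0.3 | 79.4% | 42.1% |
| 0.5 | 68.2% | 35.7% |
| 0.7 | 58.4% | 29.4% |
| 0.9 | 53.0% | 26.6% |

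At D = 0 the rate is 2.3–2.6%; with a loaded indicator it is 1.8–3.1%. A separate mixed-model fit (linear build-up, correlation 0.7, 20% spread in achieved rate, 250 simulations, rejection in either direction) gave 34% at D = 1.0.

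**Step 4: impact gains less than slow.** The slow gain is 1 SD and the impact gain is k times that (10,000 replicates). The planned slope is still significantly positive in 36.3% (k = 0.9), 24.0% (0.8), 14.6% (0.7), 7.5% (0.6) and 3.8% (0.5).

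**Step 5: the group analysis.** With equal true gains, both contrasts with control are significant in 55.9% (D = 0.8) and 79.5% (D = 1.0) of trials. If impact must also exceed slow numerically, the figures are 27.9% and 40.0%.

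**The case against.** **Adherence.** The SAP lists adherence as a potential explanatory variable. If controls were coded 0 and loaded women ranged uniformly from 0.5 to 1, it would act much like a loaded indicator: false-positive rates fall to 3.9%, 4.9% and 5.9% at D = 0.8, 1.0 and 1.5. This stands as a limit on the figures above, which apply when adherence is left out. It does not rescue the plan: adherence is only potential, its coding for controls is not stated, and it is not among the terms listed for this model.

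**Zero coding is inferred.** Zero is written for magnitude and reaches rate only through the same-plan sentence. That is true, but if it does not carry over, the control value in the rate model is undefined, which also needs correcting.

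**The group analysis is primary and implies an ordering.** Impact versus slow can be derived from its two coefficients. If the second increase must be significant relative to the lower group, equal gains would satisfy the full pattern in only 0.6–1.6% of trials at D = 0.8–1.0. The 28–40% figures rest on a weaker reading. The remaining fault here is an unnamed test and an undefined comparator.

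**Experiment 1 behaves similarly.** With equal gains at 1800 and 3600, its slope is significantly positive in 67% (D = 0.8) and 84% (D = 1.0). But zero study strain is a natural dose on the magnitude scale, so a slope from zero is a fair dose question there. In Experiment 2, not being loaded is not the low end of a rate scale among women loaded to 3600 microstrain.

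**Only the target magnitude is shared.** Achieved magnitude may differ between the impact and slow groups, and the direct contrast would carry that difference. This stands as a limit of any rate analysis in this design.

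**Conclusion.** The concern holds. As written, the continuous model's support rule for Experiment 2 does not separate a rate effect from a loading effect, and the group rule does so only through an ordering whose comparator is missing. The 0.55D false difference follows from the target rates and equal group sizes alone. The rejection rates are conditional illustrations that depend on the assumed D, time profile and correlation, and on adherence not entering as a covariate. Because loading is expected to work, the error is likely to arise in practice. It should be corrected before Experiment 2 is analysed. The data can answer the Aim 2 question; the fault is in which test is named.

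**What to change.** 1. For Experiment 2, pre-specify impact versus slow on the 12-month BMC change as the group test of the strain-rate hypothesis. Keep the two contrasts with control as tests of loading.
2. In the continuous rate model, add a loaded-versus-control indicator or fit loaded women only, and state how controls are coded. Base support for the rate hypothesis on that slope and on the contrast in item 1.
3. In Experiment 1 keep the planned slope, and pre-specify 3600 versus 1800 alongside it.
4. Report achieved strain magnitude by group in Experiment 2, so that a reader can judge whether the rate contrast is also a magnitude contrast.

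The cost is SAP wording and one model term; no new data are needed. The price is power. At 20 versus 20 the contrast has 80% power only for a difference of about 0.91 SD. If response were truly proportional to rate, with a 1 SD gain in the impact group, adding the indicator would lower power from about 93% to about 80%. The power given up came from the comparison with unloaded women, which cannot by itself distinguish rate from loading.
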